10.3.2.2. Time to Response

Time to response is defined as time from randomization to first documented CR/CRi/CRp/PR/MLFS.

Time to response will be summarized with descriptive statistics in subjects with documented CR/CRi/CRp/PR/MLFS response as determined by the IRAC. Number of subjects who attain first response in a given cycle will also be summarized. Investigator assessed results will be summarized as a supportive analysis.

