### 9.6. Efficacy Analysis

All efficacy analyses will be performed on the ITT population. Key secondary efficacy analysis will be performed on the mITT population as supportive evidence and to assess the robustness of the efficacy findings. Subjects will be analyzed according to randomized treatment group. Refer to Section 2 for the primary and secondary efficacy endpoints, respectively.

In order to perform hypothesis testing on multiple endpoints while controlling the overall Type I error rate, a closed, sequential testing approach is proposed with the endpoints to be tested in a pre-specified order. The primary efficacy endpoint of OS will be tested first at a two-sided significance level of 0.05. If superiority of AG-221 is demonstrated in OS, then each of the key secondary endpoints of overall response rate (ORR) and event-free survival (EFS), in the pre-

specified priority order will be tested, each at a two-sided 0.05 significance level once the superiority of the previous endpoint is established.

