### 9.6.2. Secondary Efficacy Analyses

The time-to-event secondary efficacy variables will be analyzed similarly to the primary efficacy variable with or without stratification when appropriate. Kaplan-Meier (KM) methods will be used to estimate time-to-event curves, unless otherwise specified. Counts and percentages will be used to describe categorical secondary variables.

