#### 9.6.2.2. Additional Secondary Efficacy Analyses

The other secondary endpoints include duration of response, time to response, rates of overall remission, CR and HI assessed by an IRAC according to modified IWG AML response criteria ([Appendix F](#)) and IWG MDS HI criteria ([Appendix H](#)), treatment mortality at 30 and 60 days, one-year survival, rate of HSCT and time to treatment failure. The definitions of these additional secondary efficacy endpoints are listed below and in Section 2.

**Duration of response** is defined as time from first documented MLFS/CR/CRi/CRp/ PR to documented morphologic relapse after CR/CRi/CRp/ PD or death due to any cause, whichever occurs first. Subjects without morphologic relapse, PD or death due to any cause will be censored at the date of the last response assessment.

**Time to response** is defined as time from randomization to first documented MLFS/CR/CRi/CRp/ /PR. Subjects without a MLFS/CR/CRi/CRp/ PR will be censored at the date of the last response assessment.

**Treatment mortality at 30 and 60 days** is defined as rate of death from any cause within 30 or 60 days of initiation of study treatment.

**One-year survival** is defined as the probability of survival at 1 year from randomization.

**Overall remission rate** is defined as rate of CR + CRi + CRp according to modified IWG AML response criteria ([Appendix F](#)).

**Complete remission rate** is defined as rate of CR according to modified IWG AML response criteria ([Appendix F](#)).

**Hematologic improvement rate** is defined as rate of neutrophil response (hematologic improvement neutrophil response [HI-N]) + platelet response (hematologic improvement platelet response [HI-P]) + erythroid response (hematologic improvement erythroid response [HI-E]) according to IWG MDS HI criteria ([Appendix H](#)).

**Rate of HSCT** is defined as rate of bridge-to-HSCT through study treatment.

**Time to treatment failure** is defined as time from randomization to discontinuation of study treatment due to any cause.

The rate of CR/CR with partial hematologic recovery (CRh; [Appendix F](#)) and duration of CR/CRh will be analyzed using the statistical methods mentioned above or other statistical methods as appropriate. Note: CRh is not available for the investigator's assessment and will be assessed by the Sponsor only and based on laboratory dataset.

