10.3. Analyses of Secondary Efficacy Endpoints

The time-to-event secondary efficacy variables will be analyzed similarly to the primary efficacy variable with and without stratification when appropriate. KM methods will be used to estimate time-to-event curves, and hazard ratio and its two-sided 95% confidence interval (CI) will be estimated from Cox proportional hazards regression model, unless otherwise specified. Counts and percentages will be used to describe categorical secondary variables.

All secondary efficacy endpoints will be analyzed based on ITT population and key efficacy analysis will be performed on the mITT population as supportive evidence and to assess the robustness of the efficacy findings. Subjects will be analyzed according to randomized treatment group.

Throughout, summaries of Complete Remission will include both CR and CRc responses, and will be displayed as CR. CRc will be summarized separately once, and otherwise will be displayed in combined categories as CR.

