10.3.2.13. Time to CR/CRh

Time to CR/CRh is defined as time from randomization to first documented CR/CRh.

Time to CR/CRh will be summarized with descriptive statistics in subjects with documented CR/CRh as determined by IRAC and sponsor assessment. It will also be summarized by cycle.

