13. CHANGES TO THE STATISTICAL ANALYSES SECTION OF THE PROTOCOL

Additional analysis of the Transfusion Independence of subjects will be conducted, which is not mentioned in the Protocol. For details see Section [10.3.2.8](#) of this SAP.

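### The SAP's time to response drops the protocol's censored non-responders without declaring the change, so its arm summaries are not a randomized comparison

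*SAP*

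**What the plan says.** **Protocol.** Section 9.6.2.2 defines time to response from randomization to the first documented MLFS, CR, CRi, CRp or PR. Subjects without a response "will be censored at the date of the last response assessment". Section 9.6 states "All efficacy analyses will be performed on the ITT population", and section 9.6.2 adds "The time-to-event secondary efficacy variables will be analyzed similarly to the primary efficacy variable with or without stratification when appropriate", with Kaplan-Meier curves unless another method is specified.

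**SAP.** Section 10.3 repeats the general rule: "The time-to-event secondary efficacy variables will be analyzed similarly to the primary efficacy variable with and without stratification when appropriate". For this endpoint, section 10.3.2.2 says "Time to response will be summarized with descriptive statistics in subjects with documented CR/CRi/CRp/PR/MLFS response as determined by the IRAC", followed by "Number of subjects who attain first response in a given cycle will also be summarized". It gives no censoring rule. Section 10.3.2.13 does the same for the CR/CRh version: "Time to CR/CRh will be summarized with descriptive statistics in subjects with documented CR/CRh as determined by IRAC and sponsor assessment".

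**Declared changes.** SAP 13 has one entry: "Additional analysis of the Transfusion Independence of subjects will be conducted, which is not mentioned in the Protocol". The change to time to response is not there.

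**The concern.** A censoring rule for subjects without a response has meaning only if those subjects are in the analysis. The SAP takes them out, so the protocol's endpoint has been replaced by a different quantity and the document's own change list is silent about it.

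The replacement conditions on having responded, which happens after randomization and may be affected by treatment. Two responder columns side by side will be read as a comparison of speed, but they describe two differently selected groups.

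The direction of the distortion can be foreseen. Protocol 7.2.1 asks investigators to aim for at least 6 cycles of AG-221, and the amendment justification that introduced this advice cites preliminary Phase 1/2 data in which response was often delayed. Each additional late responder lengthens the AG-221 responder-only time, although that subject is a gain for the arm.

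**Working it through.** Neither document gives a planning figure for time to response, the response rate or response timing. The check is therefore a comparison of the texts and an illustration with assumed counts.

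**1. The texts side by side**

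| | Protocol 9.6, 9.6.2, 9.6.2.2 | SAP 10.3.2.2 |
|---|---|---|
| Subjects | ITT, non-responders included | IRAC responders |
| Non-responders | Censored at last response assessment | Excluded |
| Method | As for OS, Kaplan-Meier by default | Descriptive statistics, by-cycle counts |
| Listed in SAP 13 | n/a | No |

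**2. Inputs.** From Protocol 9.3 and SAP 4.4: 158 subjects per arm; median OS 5.6 months (CCR) and 8 months (AG-221). These agree with the stated design: 5.6/8 = 0.70, and the required deaths are 4(1.960 + 0.842)²/(ln 0.7)² = 247 by Schoenfeld's formula and 253 by Freedman's, either side of the stated 250. Scheduled marrow assessments precede Cycles 2, 3, 5, 7 and 9 (Protocol Table 3 footnotes), that is, after 1, 2, 4, 6 and 8 cycles. The response counts below are assumptions.

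**3. More but later responses on AG-221.** First responses at 1, 2, 4, 6 and 8 cycles:

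| | CCR | AG-221 |
|---|---|---|
| First responses | 10, 5, 1, 0, 0 (16) | 12, 14, 17, 12, 8 (63) |
| Responder-only median | 1.0 cycle | 4.0 cycles |
| Responder-only mean | 24/16 = 1.5 | 244/63 = 3.9 |
| Cumulative % of 158 | 6.3, 9.5, 10.1, 10.1, 10.1 | 7.6, 16.5, 27.2, 34.8, 39.9 |

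AG-221 leads at every assessment, yet its responder-only median is 3 cycles longer. A smaller gap gives the same pattern. With 24 responders (16, 6, 2, 0, 0) against 40 (17, 8, 8, 5, 2), the medians are 1.0 and 2.0 cycles, while cumulative response runs from 10.1% to 15.2% on CCR and from 10.8% to 25.3% on AG-221.

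**4. Other timing patterns**

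- Identical timing, 16 against 64 responders: both medians are 2.0 cycles. A fourfold difference is invisible but not reversed.
- More and earlier responses on AG-221: medians 3.0 (CCR) and 2.0 (AG-221), no reversal.
- Equal numbers (24 each) with later AG-221 responses: medians 1.0 and 3.0, and AG-221 is behind until the last assessment, so the longer median is not misleading.

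**5. How often.** This was simulated with 4,000 trials per setting, the planned OS medians, one cycle taken as one month, and response hazards per cycle over cycles 0–1, 1–2, 2–4, 4–6 and 6–8. With hazards of 0.08, 0.04, 0.01, 0, 0 (CCR) and 0.10, 0.11, 0.09, 0.07, 0.05 (AG-221), the AG-221 responder median was later in 96% of trials. In 73% it was later while AG-221 was ahead or tied at every assessment. With same-shape or front-loaded hazards, that combination occurred in 16% to 18%.

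**6. Why restoring the protocol rule alone is not enough.** On the planned medians, mortality by 6 months is 1 − 2^(−6/5.6) = 52% on CCR and 1 − 2^(−6/8) = 41% on AG-221. Treating death as ordinary censoring overstates the chance of response. With the late-response hazards of step 5, one minus Kaplan-Meier at 8 cycles is 1 − exp(−0.63) = 46.7% for AG-221 and 1 − exp(−0.14) = 13.1% for CCR. The cumulative incidences, allowing for death at rate ln 2/median, are 36.6% and 11.5%.

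**The case against.** The case for leaving the SAP as it is has substance, and much of it stands.

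- **Internal contradiction.** A reader might infer that SAP 10.3.2.2 contradicts SAP 10.3. It does not: the general rule applies where appropriate and its methods sentence allows exceptions. Protocol 9.6.2 has the same latitude, and Protocol 9 leaves final methods to the SAP. That permits a change of method; it does not explain why an explicit censoring rule was dropped without an entry in SAP 13.
- **Missing denominator.** A reader might infer that the by-cycle counts have none. The general conventions point to the ITT number: Protocol 9.1 uses the population treatment group unless otherwise specified, SAP 5.1 asks for percentages and the analysis population size, and SAP 10.3 puts secondary efficacy endpoints on ITT. On that reading the counts can be summed to crude cumulative response, with deaths kept in the denominator. Section 10.3.2.2 does not confirm it, and one sentence would.
- **Time to CR/CRh.** A reader might infer that section 10.3.2.13 breaks the same rule. Protocol 9.6.2.2 gives no censoring rule for that endpoint, and Protocol Table 2 only defines it.
- **A biased test.** None is planned. The SAP names a test for the secondary endpoints it wants compared, and here it says descriptive statistics. The difference in responding is tested through ORR in ITT.
- **Validity of the summary.** How long responders took to respond is a legitimate description, and a longer figure for later responses is true. It is simply not a comparison of the arms.
- **Competing risks.** Neither document mentions this method, so it improves on the protocol's rule rather than restoring it.

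**Conclusion.** The undeclared departure is established from the text: the protocol keeps and censors non-responders, the SAP summarizes IRAC responders only, and SAP 13 does not list the change. That the responder-only columns are not a randomized comparison follows without any assumption about rates.

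The size does rest on assumptions. Under assumed counts with more but later AG-221 responses, the responder-only medians are 1 and 4 cycles (1 and 2 with a smaller gap) while AG-221 leads at every assessment. The amendment rationale makes that pattern plausible but does not establish it. A reader might infer that the endpoint will favour the wrong arm; the documents supply no response rates or timing from which to say so, and under other patterns the difference is hidden or correctly ordered.

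Time to response is a non-key secondary endpoint outside the testing hierarchy of SAP 10.1. OS, ORR, EFS, alpha and power are untouched. This is an inexpensive improvement that should be made, not a threat to the trial's conclusions.

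**What to change.** 1. In SAP 10.3.2.2, add the cumulative incidence of first response by arm in the ITT population from randomization. Count death without response as a competing event and censor other non-responders at their last response assessment.
2. State that the by-cycle first-response counts use the ITT number in each arm as denominator.
3. Keep the responder-only summary, with a statement that it is not a between-arm comparison.
4. List the departure from the protocol's censoring rule in SAP 13.
5. Use the same display for time to CR/CRh in section 10.3.2.13, for consistency rather than to correct a breach.

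Cost: one extra table and figure per endpoint and a few sentences of text. The data are already collected.

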10.3.2.3. Time to Best Response

Time to best response is defined as time from randomization to the documented best response of CR/CRi/CRp/PR/MLFS.

Time to best response will be summarized with descriptive statistics in subjects with documented CR/CRi/CRp/PR/MLFS response as determined by the IRAC. Number of subjects who attain best response in a given cycle will also be summarized. Investigator assessed results will be summarized as a supportive analysis.

10.3.2.4. Treatment Mortality at 30- and 60-Day

Treatment mortality at 30- and 60-day is defined as rate of death from any cause within 30 or 60 days of initiation of study treatment.

Number and percentage of deaths at 30- and 60-day will be summarized for each treatment arm. Treatment mortality at 30- and 60-Day will also be evaluated by KM estimate for both AG-221 and CCR treatment groups.

10.3.2.5. One-Year Survival

One-year survival is defined as the probability of survival at 1 year from randomization.

One-year survival will be evaluated by KM estimate with 95%CI for each treatment arm. Difference between the two treatment groups and corresponding two-sided 95% CI will also be displayed. The CI for the difference in the 1-year survival probabilities will be derived using Greenwood's variance estimate.

10.3.2.6. Overall Remission Rate

Overall remission rate is defined as rate of CR + CRi + CRp according to modified IWG AML response criteria per IRAC.

Number and percentage of subjects with overall remission will be summarized by treatment groups. Comparisons between AG-221 and CCR will be analyzed by Fisher's exact test. Investigator assessed results will be summarized as a supportive analysis

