4. INVESTIGATIONAL PLAN

4.1. Overall Study Design and Plan

This is an international, multicenter, open-label, randomized, Phase 3 study comparing the efficacy and safety of AG-221 versus CCRs in subjects 60 years or older with AML refractory to or relapsed after second- or third-line AML therapy and positive for an IDH2 mutation.

It is planned that approximately 316 subjects will be randomized in a 1:1 ratio to receive either the AG-221 treatment or the CCR treatment option pre-selected by the Investigator prior to randomization. Randomization will be stratified by prior intensive therapy for AML (yes versus no), primary refractory (i.e., morphologic complete remission [CR], CR with incomplete neutrophil recovery [CRi], or CR with incomplete platelet recovery [CRp] has never been attained) (yes versus no), and prior allogeneic hematopoietic stem cell transplantation (HSCT) for AML (yes versus no).

The treatment options in the CCR treatment arm include:

- BSC only: continuous 28-day cycles of BSC. Best supportive care includes, but is not limited to, hydroxyurea for leukocytosis and/or differentiation-like syndrome, anti-infectives, analgesics, antiemetics, antipyretics, transfusions and nutritional support (refer to [protocol Section 8](#) for details);
- Azacitidine SC plus BSC: continuous 28-day cycles of azacitidine 75 mg/m²/day SC for 7 days, plus BSC;
- LDAC SC plus BSC: continuous 28-day cycles of cytarabine 20 mg SC twice a day (BID) for 10 days, plus BSC;
- IDAC IV plus BSC: 28-day cycles of cytarabine 0.5 to 1.5 g/m²/day IV for 3 to 6 days, per standard institutional practice, plus BSC; only BSC given after IDAC therapy concludes per standard institutional practice.

Subjects randomized to the AG-221 treatment arm will receive AG-221 100 mg PO once a day on Days 1 to 28 of each 28-day cycle, plus BSC. Dose escalation to 200 mg may occur for augmenting treatment response.

Study treatment starts within 3 days after randomization. No crossover between any of the treatment options will be permitted during the course of study treatment per protocol.

Dosing interruptions, delays, or dose modifications may occur for managing toxicities and/or augmenting treatment response during study treatment.

[figure not shown]

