4.4. Sample Size Determination

The equality of OS curves will be compared between the AG-221 and combined CCR treatment arms using a stratified log-rank test. Subjects will be randomized to receive AG-221 treatment or a CCR treatment option pre-selected by the Investigator in a 1:1 ratio. Assuming a median OS of 5.6 months in the CCR treatment arm, a median OS of 8 months in the AG 221 treatment arm (42.9% improvement), and a drop-out rate of approximately 9%, this design requires 316 subjects (158 per treatment arm) to be randomized, and 250 deaths to be observed in order to achieve 80% power to detect a hazard ratio (HR) of 0.7 and demonstrate a statistically significant difference in OS at type I error rate of 0.05 (two-sided). It is assumed that the OS distribution is exponential with a constant failure rate and that accrual rate is 3 subjects per month for the first 12 months and 9 subjects per month afterwards. The interim analysis for superiority will be conducted at 65% information (i.e., approximately 163 deaths) based on Lan-DeMets version of the O'Brien-Fleming alpha spending function (DeMets and Lan, 2008)

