5. GENERAL STATISTICAL CONSIDERATIONS

5.1. Reporting Conventions

The following reporting conventions apply generally to tables, listings, and figures:

- Data from all study centers will be combined for analysis;
- Efficacy and Safety analyses will be done by treatment groups/options (AG-221 versus CCR overall and furthermore AG-221 versus, BSC Only, Azacitidine + BSC, LDAC + BSC, and IDAC + BSC by pre-selected CCR group). Exceptions will be noted in corresponding sections;
- All stratified efficacy analyses will use the randomization stratification factors taken from CRF (primary) including prior intensive therapy for AML (yes versus no), primary refractory (yes versus no), and prior allogeneic HSCT for AML (yes versus no) and repeated for stratification factors taken from IVRS.
- In stratified analysis, if stratified model does not converge due to small sample size, the stratification factor leads to least subjects will be dropped from the model. If a stratification factor has less than 40 subjects in one of its two levels across treatment groups, then this factor will not be used in stratified analysis;
- All statistical tests of the treatment effect will preserve a significance level of 0.05 for two-sided tests, unless otherwise specified;
- P-values will be rounded to 4 decimal places. P-values that round to 0.0000 will be presented as '<0.0001' and p-values that round to 1.000 will be presented as '>0.9999';
- Confidence intervals (CIs) will be presented as two-sided 95% CIs unless specified differently in specific analysis;
- Summary statistics will consist of the number and percentage of subjects (or cycles, if appropriate) in each category for discrete variables, and the sample size, mean, median, standard deviation, minimum, and maximum for continuous variables;
- All mean and median values will be formatted to one more decimal place than the measured value. Standard deviation values will be formatted to two more decimal places than the measured value;
- All percentages will be rounded to one decimal place. The number and percentage of responses will be presented in the form XX (XX.X%), where the percentage is in the parentheses;
- All listings will be sorted for presentation in order of treatment group, study center, subject, and date/time of procedure or event. Subjects who are screened but not randomized will be listed separately as a non-randomized group;

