10.3.1.1. Overall Response Rate

Overall response rate (ORR) is defined as the rate of Best Response in CR + CRi + CRp + partial remission (PR) + morphologic leukemia-free state (MLFS) according to modified IWG AML response criteria.

The ORR will be summarized by treatment group and be compared between arms by the Cochran-Mantel-Haenszel (CMH) test with stratification factors:

- Prior intensive therapy for AML: yes versus no
- Primary refractory: yes versus no
- Prior allogeneic HSCT for AML: yes versus no

If a stratification factor covariate has less than 40 subjects in one of its levels across treatment groups, then this factor will not be used in stratified analysis. This analysis based on IRAC assessment in the ITT population will be used as the main analysis of ORR.

As sensitivity analyses, a CMH test with the above strata will be performed in the mITT population. In addition, a Fisher's exact test without stratification factors will be performed in both ITT and mITT population. An Odds Ratio and its 95% C.I. of responders versus non-responders between treatment arms will also be calculated. This analysis will be repeated for the local assessment of response as a supportive analysis of ORR.

Additionally, overall response rate will be repeated for a Dose group analysis of AG-221 subjects who had at least one dose > 100mg during the study versus those who received only dose ≤100mg.

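### Five secondary response-type rates are compared only by unstratified Fisher's exact tests with no named between-arm estimate, which costs some power at no benefit; stratified CMH, as for ORR, would be better

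*SAP*

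**What the plan says.** SAP 10.3.2.6 (overall remission), 10.3.2.7 (CR), 10.3.2.8 (hematologic improvement), 10.3.2.9 (HSCT) and 10.3.2.11 (CR/CRh) carry the same sentence: "Comparisons between AG-221 and CCR will be analyzed by" Fisher's exact test. None of the five names strata, an odds ratio or a risk difference.

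SAP 10.3.1.1 treats ORR differently. There the rates are to "be compared between arms by the Cochran-Mantel-Haenszel (CMH) test with stratification factors", namely prior intensive therapy, primary refractory status and prior allogeneic HSCT. The unstratified Fisher test is a sensitivity analysis, and an odds ratio with a 95% CI is added.

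The factors are those of the randomization (SAP 4.1: "Randomization will be stratified by prior intensive therapy for AML (yes versus no), primary refractory", and so on). SAP 5.1 limits their use in stratified analyses: "If a stratification factor has less than 40 subjects in one of its two levels across treatment groups", that factor is left out. SAP 10.3.1.1 repeats this rule for ORR.

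The SAP 10.3 provision for analysis with and without stratification concerns time-to-event variables only. Protocol 9.6.2 foresees counts and percentages for categorical secondary variables, and protocol 9.6.2.2 leaves the CR/CRh method open.

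**The concern.** An analysis that follows a stratified randomization normally uses the strata, and ORR does so. For these five rates, the test that is only a sensitivity check for ORR becomes the sole comparison, and the SAP gives no reason.

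The split falls between nested endpoints. Overall remission (CR, CRi, CRp) is ORR without PR and MLFS, with the same independent review and the same ITT population. The two could fall on opposite sides of 0.05 partly because the test differs.

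Fisher's test also runs below its nominal level at this sample size, so real differences are missed more often than necessary. And a reader is given a p-value with no prespecified measure of how far the arms differ. Other lower-tier endpoints fare better: one-year survival has a between-arm difference with a CI (SAP 10.3.2.5), and time to treatment failure has stratified and unstratified tests and a hazard ratio (SAP 10.3.2.10).

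**Working it through.** **Inputs from the documents.** SAP 4.4: "this design requires 316 subjects (158 per treatment arm) to be randomized, and 250 deaths to be observed". SAP 10: two-sided tests at 0.05. SAP 4.1: three binary factors, so up to 2 × 2 × 2 = 8 strata. The documents give no expected rates, stratum sizes or stratum effects for the five endpoints. All of these are assumed below.

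**The plan's own power figure.** The only one is for OS, "80% power to detect a hazard ratio (HR) of 0.7". Schoenfeld's formula gives 4 × (1.960 + 0.842)² / (ln 0.7)² = 4 × 7.849 / 0.1272 ≈ 247 deaths; Freedman's gives 253. At 250 deaths, Schoenfeld power is 80.5%. The figure reproduces, but it says nothing about the five rates.

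**Step 1: Fisher against a one-stratum CMH test.** Every pair of counts (a, b) from two binomials with n = 158 was enumerated. Let m = a + b.

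- Fisher p: the sum of hypergeometric probabilities no larger than that of the observed table.
- One-stratum CMH: (a − m/2)² / [m(316 − m) / (4 × 315)], referred to chi-square on 1 df.

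True two-sided size at nominal 0.05:

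| Common rate | Fisher | One-stratum CMH |
|---|---|---|
| 5% | 0.025 | 0.049 |
| 10% | 0.033 | 0.051 |
| 20% | 0.036 | 0.049 |

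Over common rates of 2% to 40%, Fisher's size runs from 0.013 to 0.038.

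Power:

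| Assumed rates | Fisher | One-stratum CMH | Loss (points) |
|---|---|---|---|
| 3% v 10% | 65.6% | 73.3% | 7.7 |
| 5% v 13% | 65.1% | 71.7% | 6.6 |
| 10% v 20% | 65.5% | 70.8% | 5.3 |
| 20% v 33% | 71.1% | 75.1% | 4.0 |

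Other assumed pairs fall outside this range: 2% v 8% loses 10.5 points and 30% v 45% loses 3.1. Neither test uses strata here, so the whole loss is Fisher's conservatism.

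**Step 2: what stratifying adds.** Simulation, 20,000 trials per scenario, 8 strata, arms balanced within strata, control rates of 3% to 30%. Assumed factor prevalences were 70/30/10% or 70/40/20%. Each factor was given the stated odds ratio, inverted for the second factor.

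| Stratum odds ratio | Fisher to stratified CMH (points) | Of which stratification (points) |
|---|---|---|
| 1 (not prognostic) | 3.1–8.6 | about 0 |
| 1.5 | 3.9–8.7 | 0.1–0.8 |
| 2 | 5.1–9.8 | 0.4–1.7 |
| 3 | 7.9–10.9 | 1.4–4.7 |

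Example, 10% v 20%, odds ratio 2, prevalences 70/30/10%: Fisher 65.9%, unstratified chi-square 71.2%, stratified CMH 72.2%. Of the 6.3 points, 71.2 − 65.9 = 5.3 come from leaving Fisher and 72.2 − 71.2 = 1.0 from the strata.

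**Step 3: the under-40 rule.** 40/316 = 12.7%, so a factor with a level below about 12.7% of subjects is dropped. At an assumed 10% prevalence, 0.10 × 316 ≈ 32 subjects, and that factor would go. The simulation kept all three factors, so in that setting it does not reflect the rule, which could reduce the stratification part.

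**The case against.** The strongest defence is that Fisher's test is a legitimate choice here. It is valid at any count, errs on the safe side, and suits endpoints such as HSCT that may have few events. The five rates are other secondary endpoints (SAP 10.3.2), outside the OS, ORR, EFS sequence of SAP 10.1 and without a power target. The protocol asks little more than description. A like-for-like comparison with ORR already exists, because SAP 10.3.1.1 includes a Fisher test for ORR. ORR also counts PR and MLFS, so a disagreement with overall remission need not come from the method. SAP 10 calls in general for 95% CIs around intended point estimates. And eight strata with an under-40 rule may leave little to stratify on.

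Most of this stands, and it keeps the point minor. It does not remove two things. The general CI sentence helps only where an estimate is named, and these sections name no between-arm estimate. And Fisher's conservatism costs power with nothing gained over the rates examined, where the one-stratum CMH test holds its size at 0.045 to 0.051.

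A reader might infer that the 4 to 8 points are the price of ignoring the randomization strata. The calculation does not support that: the comparator in Step 1 has one stratum, and an unstratified chi-square would recover most of the loss.

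**Conclusion.** The concern holds as a minor inefficiency and an inconsistency with the ORR analysis. At 158 per arm and the four assumed rate pairs, Fisher's test gives up about 4 to 8 points of power because its true size is about 0.025 to 0.036 rather than 0.05. Stratifying would add under about 2 points for stratum odds ratios up to 2, and up to about 5 only if all three factors had odds ratios near 3. The sizes depend on assumed rates, prevalences and stratum effects and are not a property that can be read from the plan. The absence of a named between-arm estimate needs no assumption.

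Two stronger readings should be resisted. The tests are not invalid: type I error is below nominal, not inflated. Nor are these the main supporting efficacy results: SAP 10.3.1 gives that place to ORR and EFS. No confirmatory conclusion and no stated power figure changes.

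**What to change.** In SAP 10.3.2.6 to 10.3.2.9 and 10.3.2.11, before database lock:

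- make the stratified CMH test of SAP 10.3.1.1, with the same under-40 rule, the main between-arm comparison;
- report a stratified odds ratio or risk difference with a two-sided 95% CI, and say which (the ORR odds ratio in 10.3.1.1 is not stated to be stratified, so this should be made explicit);
- keep Fisher's exact test as a sensitivity analysis, or for sparse counts under a rule fixed in advance.

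The cost is a short SAP edit and reuse of the ORR program. No new data are needed, and the sample size and testing sequence are untouched.
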